Endpoint	Primary outcome: Median monthly convulsive seizure frequency Secondary outcomes: 1. Caregiver/Investigator Global Impression of Change (C/IGIC). The parent/caregiver and investigator rated change on a 7-point scale: 1-very much improved; 2-much improved; 3-minimally improved; 4-no change; 5-minimally worse; 6-much worse; and 7-very much worse 2. Quality of Life in Childhood Epilepsy Scale (13). A low-burden parent/caregiver completed assessment that looks at how epilepsy affects day-to-day functioning of their child in various life areas, including physical activities, well-being, cognition, social activities, behavior and general health. 3. Pediatric Quality Of Life Inventory (PEDS-QL). A parent/caregiver completed assessment that looks at how epilepsy affects day-to-day functioning of their child in various life areas, including physical activities, well-being, cognition, social activities, behavior and general health during a specific time frame		
Study Duration	14 weeks with extension available		
Duration of IP administration	14 weeks with extension available		
Population	confirmed genetic/clinical diagnosis of CDKL5 Deficiency Disorder (CDD)		
Study Sites	1: NYU Comprehensive Epilepsy Center.		
Number of participants	10 patients: 7: ages 2-18 years old Max of 3: ages 18-35 years old		
Description of Study Agent	Liquid		
Key Procedures	Blood draws, questionnaires, Doppler echocardiogram, electrocardiogram		

Page 2 Study number: s18-01530

Version: 11 Jan 20									
Protocol Activity: Week (±7 days)	Baseline Week 0	Safety call	Week 2	Week 6	Safety call	Week 10	Safety call	Week 14	Post Taper Follow up
Visit	1	Safety call	2	3	Safety call	4	Safety call	5/End of study/ End of treatment/ Withdrawal visit	
Informed consent/assent	X								
Inclusion/exclusion criteria	X	X	X	X	X	X	X	X	
Medical history	X	X	X	X	X	X	X	X	X
Demographics	X		I	I.	I .	I	1	T	
Physical and neurological exam and Vital signs	X		X	X		X		X	
Adverse events	X	X	X	X	X	X	X	X	X
EKG	X			X				X	
Echo	X		37	X		37		X	
C/IGIC	X		X	X		X		X	
QOLCE PEDS-QOL	X		X	X		X		X	
Hematology & Chemistry (draw/handling) (CBC, CMP, LFTs, BUN, Creatinine), Coagulation	X		X	X		X		X	
HCG (urine and serum)	X		X	X		X		X	
THC (urine and serum)	X		X	X		X		X	
Urinalysis	X		X	X		X		X	
AED levels /Clobazam	X			X		X		X	
Study diary provided	X		X	X		X		X	
Study diary collected			X	X		X		X	
Study drug dispensed	X		X	X		X		X*	
Study Drug administration	X								

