Study drug compliance dosing schedule and return dosing schedule	X	X	X	X	X	X	X	X	X
Concomitant/other medications/supplements	X	X	X	X	X	X	X	X	X

Version: 11 Jan 2021

				Exte	ension			
Protocol Activity: Week (±7 days)	Exten sion Visit	Safety call	Extension Visit	Safety call	Extension Visit	Safety call	End of Treatment/ Withdrawal	Post Taper Follow up
Inclusion/excl usion criteria	X	X	X	X	X	X	X	
Medical history	X	X	X	X	X	X	X	X
Physical and neurological exam and Vital signs	X		X		X		X	
Adverse events	X	X	X	X	X	X	X	X
EKG	X		X		X		X	
Echo	X		X		X		X	
C/IGIC	X		X		X		X	
QOLCE	X		X		X		X	
PEDS-QOL	X		X		X		X	
Hematology & Chemistry (draw/handlin g) (CBC, CMP, LFTs, BUN, Creatinine), Coagulation	X		X		X		X	
HCG (urine and serum)	X		X		X		X	
THC (urine and serum)	X		X		X		X	
Urinalysis	X		X		X		X	
AED levels /Clobazam	X		X		X		X	
Study diary provided	X		X		X		X	
Study diary collected	X		X		X		X	
Study dispensed	X		X		X		X	
Study drug compliance dosing schedule and return dosing schedule	X	X	X	X	X	X	X	X
Concomitant/ other medications/s upplements	X	X	X	X	X	X	X	X

^{*}If subject continues to extension visit

Version: 11 Jan 2021

1. Key Roles

Principal Investigator: [name]

New York University Comprehensive Epilepsy Center

[name] US [contact]

Email: [contact]

2. Introduction, Background Information and Scientific Rationale

2.1Background Information and Relevant Literature: Name and Description of the Investigational Agent

Fenfluramine is an amphetamine analogue that was synthesized many years ago. It was approved in a large number of countries and widely prescribed as an appetite suppressant for the treatment of adult obesity. Brand names for fenfluramine formulations included Ponderax and Pondimin. Fenfluramine was also used extensively in an off-label combination with phentermine ("Fen-Phen") to treat adult obesity. Fenfluramine is a racemic compound and the single enantiomer D-fenfluramine (dexfenfluramine) was also approved and marketed for the treatment of obesity as Adifax, Redux, and others.

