6.1.7 Taper Period

Subjects will decrease from 0.8 mg/kg BID to a dose of 0.4 mg/kg BID (maximum 30 mg/day or). After 4 days at this dose level, subjects will decrease their dose to 0.2 mg/kg/day. On Study Day 9, all subjects will stop taking study medication. The taper is expected to take a total of 8 days.

Taper schedule					
	Day 5-8 after end of	Day 9-14 after end of			
	study/ study	study/ study			
	withdrawal	withdrawal			
	ZX008 0.4 mg/kg/day	ZX008 0.2 mg/kg/day			

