- Complete the following assessments:
 - Caregiver and Investigator Global Impression of Change
 - QOLCE
 - o PEDS-QOL

Study number: s18-01530 Page 21 Version: 11 Jan 2021

• Blood draw for Complete blood count (CBC), comprehensive metabolic panel (CMP) Serum/Urine human chorionic gonadotropin (HCG), as applicable (sample taken only for female subjects of childbearing potential), and antiepileptic medication levels

- Urinalysis
- Urine or serum THC
- Dispense new seizure diary and review instructions for completion
- Dispense study drug and review administration instructions
- Instruct subject to return in 4 weeks for Visit 5

Safety call telephone

The safety call will occur between visit 4 and visit 5. It will proceed as follows:

- Record any AEs occurring since last visit and any that occur during this visit
- Record any changes in concomitant medications

Visit 5/End of study/ End of treatment/ Withdrawal visit (Week 14)

Visit 5 will proceed as follows:

- Physical and neurological examination and height and weight
- Vital signs (including systolic and diastolic blood pressure, radial pulse rate, and body temperature): performed after the subject has been in a sitting position for 3–5 minutes
- EKG and echocardiogram
- Collect seizure diary and review entries
- Record any AEs occurring since last visit and any that occur during this visit
- Record any changes in concomitant medications
- Complete the following assessments:
 - o Caregiver and Investigator Global Impression of Change
 - o OOLCE
 - o PEDS-QOL
- Blood draw for Complete blood count (CBC), comprehensive metabolic panel (CMP) Serum/Urine human chorionic gonadotropin (HCG), as applicable (sample taken only for female subjects of childbearing potential), and antiepileptic medication levels
- Urinalysis
- Urine or serum THC
- For those subjects who have responded (response level ≥ 40%) and will like to continue in to the extension study:
 - o Dispense new seizure diary and review instructions for completion
 - o Dispense study drug and review administration instructions
 - o Instruct subject to return in 12 weeks for Extension visit 1
- For those subjects who have not responded and will not continue in to the extension study:
 - o Taper schedule will be given
 - O Subject have final post taper follow up in 4 weeks after the last dose

Version: 11 Jan 2021 7.5.2 Extension

Extension visits

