7.5.3 End of treatment

End of treatment/ Withdrawal visit

End of treatment/withdrawal will proceed as follows:

- Physical and neurological examination and height and weight
- Vital signs (including systolic and diastolic blood pressure, radial pulse rate, and body temperature): performed after the subject has been in a sitting position for 3–5 minutes
- EKG and echocardiogram
- Collect seizure diary and review entries
- Record any AEs occurring since last visit and any that occur during this visit

Version: 11 Jan 2021Record any changes in concomitant medications

- Complete the following assessments:
 - Clinical Caregiver/Investigator Global Impression of Change
 - QOLCE
 - o PEDS-QOL
- Blood draw for Complete blood count (CBC), comprehensive metabolic panel (CMP) Serum/Urine human chorionic gonadotropin (HCG), as applicable (sample taken only for female subjects of childbearing potential), and antiepileptic medication levels
- Urinalysis
- Urine or serum THC
- Subject have final post taper follow up in 4 weeks after the last dose

Post Taper Follow-up

The Follow-up visit is to occur 4 weeks after the last dose of study drug, It will proceed as follows:

- Record any AEs occurring since last visit and any that occur during this visit
- Record any changes in concomitant medications
- Return any study medications

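### Week 14 dispensing is limited to patients entering the extension, yet patients who leave at Visit 5 are put on a stepped taper for which no drug supply is named

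*Combined protocol and SAP*

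**What the plan says.** **Core schedule (Protocol Summary).** The row "Study drug dispensed" is marked at Weeks 0, 2, 6 and 10 without qualification. At Week 14 the mark carries an asterisk, and the footnote, printed below the extension schedule, reads "If subject continues to extension visit".

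**Visit 5 (Section 7.5.1).** Patients with a response of at least 40% who wish to continue have the line "Dispense study drug and review administration instructions". The other branch opens "For those subjects who have not responded and will not continue in to the extension study" and lists only "Taper schedule will be given" and a follow-up 4 weeks after the last dose.

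**Visit 4 (Week 10).** This is the last unconditional dispensing before Week 14. It ends with "Instruct subject to return in 4 weeks for Visit 5" and states no quantity.

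**Section 6.1.7.** The taper has two dose levels: "After 4 days at this dose level, subjects will decrease their dose to 0.2 mg/kg/day". The text gives 8 days in total and writes the first step per BID dose. The table beside it writes that step per day and runs over Days 5-8 and 9-14.

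**Extension.** The extension schedule marks dispensing at End of Treatment/Withdrawal with no asterisk. The Section 7.5.3 procedures for that visit include no dispensing. At the post-taper follow-up, the same section lists "Return any study medications".

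**The concern.** A stepped taper needs drug. The schedule and the visit text both confine Week 14 dispensing to patients who continue, so this reads as an operative instruction and not a slip in one table. The extension schedule treats the same event, leaving treatment, in the opposite way, and its own visit text does not support it.

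A site that follows the core schedule exactly sends a departing patient home with a taper schedule and whatever drug remains. If that is too little, the taper is cut short in a patient with refractory epilepsy without anyone having decided so. In a study of 10 patients with descriptive analysis only (Sections 9.1 and 9.2), even one such case would complicate the reading of adverse events recorded at the post-taper follow-up.

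A responder who declines the extension fits neither Visit 5 branch, and so has neither a dispensing line nor a taper line.

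**Working it through.** The protocol gives no supply calculation to reproduce. The check asks whether leftover Visit 4 drug would cover the taper.

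**Inputs from the protocol**
- Solution of 2.5 mg/mL in 120 mL bottles (Section 6.1.2), so 300 mg per bottle.
- Maintenance dose of 0.8 mg/kg/day, at most 30 mg/day (Section 6.1.6). The cap is reached at 30/0.8 = 37.5 kg.
- 28 days from Visit 4 to Visit 5, with a window of ±7 days (schedule).

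**Assumptions, not in the protocol:** body weights; fewest whole bottles for the planned days; no carry-over from earlier visits; every dose taken with no spillage; taper calculated on actual weight.

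**Formulas**
- Daily volume = min(0.8 × W, 30)/2.5 mL.
- Leftover = bottles × 120 − days × daily volume.
- 8-day taper read as mg/kg/day = (4 × 0.4 + 4 × 0.2) × W/2.5 = 0.96 × W mL.

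**28-day supply, visit on day 28**

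| Weight (kg) | mL/day | 28-day use (mL) | Bottles (mL) | Left (mL) | Taper need (mL) | Enough? |
|---|---|---|---|---|---|---|
| 13 | 4.16 | 116.5 | 1 (120) | 3.5 | 12.5 | No |
| 20 | 6.40 | 179.2 | 2 (240) | 60.8 | 19.2 | Yes |
| 26 | 8.32 | 233.0 | 2 (240) | 7.0 | 25.0 | No |
| 37.5 | 12.00 | 336.0 | 3 (360) | 24.0 | 36.0 | No |

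**Which weights are short.** Below the cap, 28 days use 8.96 × W mL and the taper adds 0.96 × W, in total 9.92 × W. The leftover is short when 9.92 × W exceeds the whole bottles that cover 8.96 × W:
- one bottle: 120/9.92 = 12.1 to 120/8.96 = 13.4 kg;
- two bottles: 240/9.92 = 24.2 to 240/8.96 = 26.8 kg;
- three bottles: from 360/9.92 = 36.3 kg up to the cap at 37.5 kg.

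Above the cap the leftover stays at 24 mL and the need is at least 36 mL, so every weight is short.

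**Sensitivity to supply and timing, same taper reading**
- *35-day supply, day-28 visit:* 123.5, 60.8, 127.0 and 144.0 mL are left at 13, 20, 26 and 37.5 kg. All are enough, as is every whole-kg weight from 10 to 70.
- *28-day supply, day-35 visit:* 20 kg leaves 240 − 35 × 6.4 = 16 mL against 19.2 mL. At 13, 26 and 37.5 kg the bottles run out before the visit. Of the 61 whole-kg weights from 10 to 70, 52 are short.
- *35-day supply, day-35 visit:* 20 kg again leaves 16 mL against 19.2 mL; 37.5 kg leaves 480 − 420 = 60 mL against 36 mL.

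**Sensitivity to the reading of Section 6.1.7, at 37.5 kg**
- 8 days, both steps per day: 2.4 mg/kg = 90 mg = 36 mL.
- Table, Days 5-14: 4 × 0.4 + 6 × 0.2 = 2.8 mg/kg = 105 mg = 42 mL.
- First step read as 0.4 mg/kg BID: 4 × 0.8 + 4 × 0.2 = 4.0 mg/kg = 150 mg = 60 mL.
- Table, with its unlisted Days 1-4 assumed to be at the maintenance dose: 4 × 0.8 + 2.8 = 6.0 mg/kg = 225 mg = 90 mL.

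**The case against.** A reader might infer that departing patients have no drug for the taper, that all of them are exposed, or that they will stop abruptly. The documents do not support any of these. The Visit 4 quantity is not stated, the Visit 5 text collects no drug, and Section 7.5.3 places "Return any study medications" at the follow-up after the taper, which fits patients holding drug until then. The 20 kg case has enough even on the minimum supply.

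The shortfall is also produced by an assumption. With a ±7-day window, a site might sensibly dispense 35 days, and a day-28 visit then covers the 8-day taper. Carry-over could help too. On the same bottle rule, Visit 1 dispensing at 37.5 kg leaves 300 − (4 × 7.5 + 4 × 15 + 6 × 30) = 30 mg, and each of Visits 2-4 leaves 900 − 840 = 60 mg. That is 210 mg in all if kept, against 90 mg needed. Whether it is kept is unclear, since Visit 3 reviews returned drug.

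Further, Section 5.6.1 lets the method of stopping depend on the reason for withdrawal and provides for a discussion with the family, so not every withdrawal needs a taper supply. The schedule marks drug compliance at the post-taper follow-up, so an incomplete taper could be detected. Section 6.1.2 points to separate handling instructions that are not available here.

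All of this limits the consequence. None of it removes the conflict: Week 14 dispensing is expressly restricted, a taper is prescribed, and the extension schedule and its text disagree.

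**Conclusion.** The conflict holds. Dispensing at Week 14 is limited to patients who continue, patients who leave are given a taper, and no supply for it is named. The extension schedule and Section 7.5.3 contradict each other on the same point.

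The size of the consequence is conditional. On a minimum 28-day whole-bottle supply with no carry-over and a day-28 visit, the 8-day taper read as mg/kg/day is uncovered in three narrow weight bands below 37.5 kg and at all weights above it. A late visit on that supply widens the shortfall; a 35-day supply with a day-28 visit removes it. Whether a patient can complete the taper thus depends on weight, bottle rounding, visit timing and an unstated quantity. An unintended abrupt stop is a possibility that the protocol leaves open, not one it states or makes certain.

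**What to change.** Reconcile the core schedule and its Week 14 footnote, the extension schedule, Section 6.1.7, the Visit 5 text and Section 7.5.3, so that all of them agree on how drug is supplied for whatever taper the protocol requires. Provide for responders who decline the extension, who currently fall outside both Visit 5 branches. Record the volumes dispensed and returned, so that completion of the taper can be verified.

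The taper levels, units and days in Section 6.1.7 must be reconciled as well, because the volume needed cannot be fixed until they are. No dose or taper rule is proposed here.

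The cost is a small amendment to a footnote, the schedule entries and a few lines of visit text, and at most about one extra bottle per tapering patient: at 37.5 kg, one 120 mL bottle exceeds even the 90 mL of the longest reading above.

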7.5.3 End of treatment

End of treatment/ Withdrawal visit

End of treatment/withdrawal will proceed as follows:

- Physical and neurological examination and height and weight
- Vital signs (including systolic and diastolic blood pressure, radial pulse rate, and body temperature): performed after the subject has been in a sitting position for 3–5 minutes
- EKG and echocardiogram
- Collect seizure diary and review entries
- Record any AEs occurring since last visit and any that occur during this visit

Version: 11 Jan 2021Record any changes in concomitant medications

- Complete the following assessments:
 - Clinical Caregiver/Investigator Global Impression of Change
 - QOLCE
 - o PEDS-QOL
- Blood draw for Complete blood count (CBC), comprehensive metabolic panel (CMP) Serum/Urine human chorionic gonadotropin (HCG), as applicable (sample taken only for female subjects of childbearing potential), and antiepileptic medication levels
- Urinalysis
- Urine or serum THC
- Subject have final post taper follow up in 4 weeks after the last dose

Post Taper Follow-up

The Follow-up visit is to occur 4 weeks after the last dose of study drug, It will proceed as follows:

- Record any AEs occurring since last visit and any that occur during this visit
- Record any changes in concomitant medications
- Return any study medications

7.5.4 Unscheduled Visit

- Record any AEs occurring since last visit and any that occur during this visit
- Record any changes in concomitant medications

7.6 Concomitant Medications

All concomitant prescription medications taken during study participation will be recorded on the case report forms (CRFs). For this protocol, a prescription medication is defined as a medication that can be prescribed only by a properly authorized/licensed clinician. Medications to be reported in the CRF are concomitant prescription medications, over-the-counter medications and non-prescription medications. Epidiolex is only acceptable CBD preparation that may be included. All other formulations are excluded.

7.7 Prohibited Medications, Treatments, and Procedures

Treatment with other investigational medications will not be permitted.

7.8 Participant Access to Study Agent at Study Closure

Zogenix will continue to supply study medication to those subjects that received benefit from the study after participant are no longer enrolled in the study.

8 Assessment of Safety

8.1 Specification of Safety Parameters

• Treatment-emergent adverse events will be continuously reported throughout the study CONFIDENTIAL

Version: 11 Jan 2021

• Each patient will undergo a Doppler echocardiographic (ECHO) and ECG examinations during the baseline period and again at weeks 6, 14, and every 3 months thereafter during the extension study and End of treatment/withdrawal visits.

• All ECHOs readings will be sent to the site for evaluation and will be graded as to presence and severity of cardiac valve regurgitation

8.1.1 Definition of Adverse Events (AE)

An *adverse event* (AE) is any symptom, sign, illness or experience that develops or worsens in severity during the course of the study. Intercurrent illnesses or injuries should be regarded as adverse events. Abnormal results of diagnostic procedures are considered to be adverse events if the abnormality:

- results in study withdrawal
- is associated with a serious adverse event
- is associated with clinical signs or symptoms
- leads to additional treatment or to further diagnostic tests
- is considered by the investigator to be of clinical significance

8.1.2 Definition of Serious Adverse Events (SAE)

Serious Adverse Event

Adverse events are classified as serious or non-serious. A *serious adverse event* is any AE that is:

- fatal
- life-threatening
- requires or prolongs hospital stay
- results in persistent or significant disability or incapacity
- a congenital anomaly or birth defect
- an important medical event

Important medical events are those that may not be immediately life threatening, but are clearly of major clinical significance. They may jeopardize the subject, and may require intervention to prevent one of the other serious outcomes noted above. For example, drug overdose or abuse, a seizure that did not result in in-patient hospitalization, or intensive treatment of bronchospasm in an emergency department would typically be considered serious.

All adverse events that do not meet any of the criteria for serious should be regarded as **non-serious adverse events**.

8.1.3 Definition of Unanticipated Problems (UP)

Unanticipated Problems Involving Risk to Subjects or Others

Any incident, experience, or outcome that meets all of the following criteria:

- Unexpected in nature, severity, or frequency (i.e. not described in study-related documents such as the IRB-approved protocol or consent form, the investigators brochure, etc)
- Related or possibly related to participation in the research (i.e. possibly related means there is a reasonable possibility that the incident experience, or outcome may have been

Version: 11 Jan 2021

caused by the procedures involved in the research)

• Suggests that the research places subjects or others at greater risk of harm (including physical, psychological, economic, or social harm).

8.2 Classification of an Adverse Event

8.2.1 Severity of Event

The following grading system will be used to describe severity.

- **Grade 1: Mild** Events require minimal or no treatment and do not interfere with the participant's daily activities.
- **Grade 2: Moderate** Events result in a low level of inconvenience or concern with the therapeutic measures. Moderate events may cause some interference with functioning.
- **Grade 3: Severe** Events interrupt a participant's usual daily activity and may require systemic drug therapy or other treatment. Severe events are usually potentially lifethreatening or incapacitating.

8.2.2 Relationship to Study Agent

The clinician's assessment of an AE's relationship to study agent (drug, biologic, device) is part of the documentation process, but it is not a factor in determining what is or is not reported in the study. If there is any doubt as to whether a clinical observation is an AE, the event should be reported. All AEs must have their relationship to study agent assessed. In a clinical trial, the study product must always be suspect. To help assess, the following guidelines are used:

- **Related** The AE is known to occur with the study agent, there is a reasonable possibility that the study agent caused the AE, or there is a temporal relationship between the study agent and event. Reasonable possibility means that there is evidence to suggest a causal relationship between the study agent and the AE.
- **Not Related** There is not a reasonable possibility that the administration of the study agent caused the event, there is no temporal relationship between the study agent and event onset, or an alternate etiology has been established.

For all collected AEs, the clinician who examines and evaluates the participant will determine the AE's causality based on temporal relationship and his/her clinical judgment. The degree of certainty about causality will be graded using the categories below:

- **Definitely Related** There is clear evidence to suggest a causal relationship, and other possible contributing factors can be ruled out. The clinical event, including an abnormal laboratory test result, occurs in a plausible time relationship to drug administration and cannot be explained by concurrent disease or other drugs or chemicals. The response to withdrawal of the drug (dechallenge) should be clinically plausible. The event must be pharmacologically or phenomenologically definitive, with use of a satisfactory rechallenge procedure if necessary.
- **Probably Related** There is evidence to suggest a causal relationship, and the influence of other factors is unlikely. The clinical event, including an abnormal laboratory test result, occurs within a reasonable time after administration of the drug, is unlikely to be

Version: 11 Jan 2021 attributed to concurrent disease or other drugs or chemicals, and follows a clinically reasonable response on withdrawal (dechallenge). Rechallenge information is not required

to fulfill this definition.

• **Possibly Related** – There is some evidence to suggest a causal relationship (e.g., the event occurred within a reasonable time after administration of the trial medication). However, other factors may have contributed to the event (e.g., the participant's clinical condition, other concomitant events). Although an AE may rate only as "possibly related" soon after discovery, it can be flagged as requiring more information and later be upgraded to "probably related" or "definitely related," as appropriate.

- Unlikely to be related A clinical event, including an abnormal laboratory test result, whose temporal relationship to drug administration makes a causal relationship improbable (e.g., the event did not occur within a reasonable time after administration of the trial medication) and in which other drugs or chemicals or underlying disease provides plausible explanations (e.g., the participant's clinical condition, other concomitant treatments).
- **Not Related** The AE is completely independent of study drug administration, and/or evidence exists that the event is definitely related to another etiology. There must be an alternative, definitive etiology documented by the clinician.

